1.1 Synopsis

AbbVie Inc.	Protocol Number: M14-567
Name of Study Drug: Ombitasvir, ABT-450, ritonavir, sofosbuvir, ribavirin	Phase of Development: 2
Name of Active Ingredient: ombitasvir: Dimethyl [(2S,5S)-1-(4- tert -butylphenyl) pyrrolidine-2,5-diyl]bis{benzene-4,1-diylcarbamoyl(2S)pyrrolidine-2,1-diyl[(2S)-3-methyl-1-oxobutane-1,2-diyl]})biscarbamate hydrate ABT-450: (2R,6S,12Z,13aS,14aR,16aS)-N-(cyclopropylsulfonyl)-6-{[(5-methylpyrazin-2-yl)carbonyl]amino}-5,16-dioxo-2-(phenanthridin-6-yloxy)-1,2,3,6,7,8,9,10,11,13a,14,15,16,16a-tetradecahydrocyclopropa[e]pyrrolo[1,2-a][1,4]diazacyclopentadecine-14a(5H)-carboxamide hydrate ritonavir: 10-Hydroxy-2-methyl-5-(1-methylethyl)-1-[2-(1-methylethyl)-4-thiazolyl]-3,6-dioxo-8,11-bis(phenylmethyl)-2,4,7,12-tetraazatridecan-13-oic acid, 5-thiazolylmethyl ester, [5S-(5R*,8R*,10R*,11R*)] sofosbuvir: (S)-Isopropyl 2-((S)-(((2R,3R,4R,5R)-5-(2,4-dioxo-3,4-dihydropyrimidin-1(2H)-yl)-4-fluoro-3-hydroxy-4-methyltetrahydrofuran-2-yl)methoxy)-(phenoxy)phosphorylamino)propanoate ribavirin: 1- β -D-ribofuranosyl-1H-1,2,4-triazole-3-carboxamide	Date of Protocol Synopsis: 31 July 2014
Protocol Title: A Randomized, Open-Label Study to Evaluate the Safety and Efficacy of the Co-Administration of Ombitasvir/ABT-450/Ritonavir (Ombitasvir/ABT-450/r) With Sofosbuvir (SOF) With or Without Ribavirin (RBV) in Subjects With Genotype 3 Chronic Hepatitis C Virus (HCV) Infection	

Objectives:

The primary objectives of this study are to assess the safety and efficacy (the percentage of subjects achieving a 12-week sustained virologic response ([SVR₁₂] [HCV ribonucleic acid (RNA) < lower limit of quantification (LLOQ) 12 weeks following treatment]) of co-formulated ombitasvir with ABT-450 and ritonavir (r) (ombitasvir/ABT-450/r) co-administered with sofosbuvir (SOF) with or without ribavirin (RBV) in treatment-naïve and prior (pegIFN, RBV, and/or SOF) treatment-experienced adults with genotype 3 HCV infection without cirrhosis.

The secondary objectives of this study are to assess the percentage of subjects with virologic failure during treatment, the percentage of subjects with post-treatment relapse, and to characterize the pharmacokinetics of direct-acting antiviral agents (DAAs) including ritonavir, SOF, GS-331007 (predominant circulating metabolite of SOF), and RBV (if applicable) in adults with genotype 3 HCV infection.

Investigators: Multicenter, investigator information on file at AbbVie

Study Sites: Approximately 8 sites

Study Population: Adult males and females at least 18 years of age with HCV genotype 3 infection without cirrhosis, who are treatment-naïve or previously treated with pegIFN, RBV, and/or SOF.

Number of Subjects to be Enrolled: Approximately 20 subjects.

Methodology:

This is a Phase 2, randomized, open-label, multicenter study evaluating the safety and efficacy of co-formulated ombitasvir/ABT-450/r co-administered with SOF with or without RBV in treatment naïve and prior (pegIFN, RBV, and/or SOF) treatment-experienced adults with genotype 3 HCV infection without cirrhosis. Approximately 20 subjects will be enrolled across approximately 8 sites globally into one of two arms.

The study consists of:

- **Treatment Period:** Approximately 20 subjects with genotype 3 HCV infection will be randomized 1:1 into the following treatment arms (approximately 10 subjects each):
 - **Arm A:** ombitasvir/ABT-450/r 25 mg/150 mg/100 mg once daily (QD) + SOF 400 mg QD for 12 weeks
 - **Arm B:** ombitasvir/ABT-450/r 25 mg/150 mg/100 mg QD + SOF 400 mg QD + RBV 1000 – 1200 mg divided twice daily (BID) for 12 weeks.Randomization to Arms A and B will be stratified by IL28B genotype (CC versus non-CC) and prior treatment status (treatment-naïve versus treatment-experienced). Study drugs should be administered with food. Subject safety laboratory results and virologic failure criteria will be evaluated during the Treatment Period. Upon completion of the Treatment Period or premature discontinuation, subjects will enter the Post-Treatment (PT) Period.
- **PT Period:** Subjects who complete or prematurely discontinue study drugs in the Treatment Period will be followed for 48 weeks to monitor safety, HCV RNA, the emergence and persistence of resistant viral variants, and assessments of Patient Report Outcomes (PROs).

Methodology (Continued):**Virologic Failure Criteria for Subject Management:**

The following criteria will be considered evidence of virologic failure. Subjects demonstrating any of the following will be discontinued from study drug:

- Confirmed increase from nadir in HCV RNA (defined as 2 consecutive HCV RNA measurements of $> 1 \log_{10}$ IU/mL above nadir) at any time point during treatment; or
- Failure to achieve HCV RNA $<$ LLOQ by Week 8; or
- Confirmed HCV RNA \geq LLOQ (defined as 2 consecutive HCV RNA measurements \geq LLOQ) at any point during treatment after HCV RNA $<$ LLOQ.

Confirmatory testing, where required, should be completed as soon as possible. Also, when confirmation is required, the subject should remain on study treatment until the virologic failure has been confirmed.

If any of the above criteria are met on therapy, the subject will discontinue study treatment as described above.

All subjects who receive at least one dose of study drug in the Treatment Period will be monitored in the Post-Treatment Period for up to 48 weeks following the last dose of study drug.

Diagnosis and Main Criteria for Inclusion/Exclusion:**Main Inclusion:**

1. Male or female at least 18 years of age at time of screening.
2. Chronic HCV infection prior to study enrollment. Chronic HCV infection is defined as one of the following:
 - Positive for anti-HCV Antibody (Ab) or HCV RNA at least 6 months before Screening, and positive for HCV RNA and anti-HCV Ab at the time of Screening; or
 - HCV RNA $> 10,000$ IU/mL at the time of Screening with a liver biopsy consistent with chronic HCV infection (or a liver biopsy performed prior to enrollment with evidence of chronic hepatitis C disease).
3. Screening laboratory results from the central clinical laboratory indicating HCV genotype 3 infection only.
4. Subjects must be able to understand and adhere to the study visit schedule and all other protocol requirements and must voluntarily sign and date an informed consent.
5. Absence of cirrhosis, as documented by meeting one of the following criteria (per local standard practice):
 - Liver biopsy within 24 months prior to screening or during screening demonstrating the absence of cirrhosis.
 - Only in the absence of a biopsy within the 24 months prior to screening or during screening:
 - a screening FibroTest score of ≤ 0.72 and Aspartate Aminotransferase to Platelet Ratio Index (APRI) ≤ 2 ; or
 - a screening transient elastography (e.g., FibroScan[®]) result of < 12.5 kPa.

Diagnosis and Main Criteria for Inclusion/Exclusion (Continued):**Main Inclusion(Continued):**

Subjects with a FibroScan® result that is ≥ 12.5 kPa and < 14.6 kPa, **or** a FibroTest result that is ≤ 0.72 and an APRI ≥ 2 , **or** a FibroTest result that is > 0.73 and an APRI ≤ 2 , must have a liver biopsy performed within 24 months prior to screening showing no evidence of cirrhosis, or in the absence of an available biopsy results within 24 months prior to screening, may undergo a liver biopsy during screening to rule out cirrhosis.

Main Exclusion:

1. Females who are pregnant or plan to become pregnant or breastfeeding, or males whose partners are pregnant or planning to become pregnant within 7 months (or per local RBV label) after their last dose of study drug.
2. Recent (within 6 months prior to study drug administration) history of drug or alcohol abuse that could preclude adherence to the protocol.
3. Positive test result for Hepatitis B surface antigen (HbsAg) or anti-HIV Ab positive.
4. Current enrollment in another clinical study, previous enrolment in this study, or previous use of any investigational or commercially available anti-HCV therapy (other than interferon, pegIFN, RBV, and or SOF) including previous exposure to telaprevir, boceprevir, ABT-450, or ombitasvir (ABT-267). Subjects who previously participated in trials of investigational anti-HCV agents may be enrolled with approval of the AbbVie Study Designated Physician if they can produce documentation that they received only placebo. Concurrent participation in a non-interventional, epidemiologic, or registry trial may be permitted with approval by the AbbVie Study Designated Physician.
5. Any current or past clinical evidence of cirrhosis such as ascites or esophageal varices, or prior biopsy showing cirrhosis, e.g., a Metavir score > 3 or an Ishak score > 4 .
6. Screening laboratory analyses showing any of the following abnormal laboratory results:
 - Calculated creatinine clearance (using Cockcroft-Gault method) < 30 mL/min.
 - Albumin $<$ Lower limit of normal (LLN).
 - Prothrombin time/International normalized ratio (INR) > 1.5 . Subjects with a known inherited blood disorder and INR > 1.5 may be enrolled with permission of the AbbVie Study Designated Physician.
 - Hemoglobin $<$ LLN.
 - Platelets $< 120,000$ cells per mm^3 .
 - Absolute neutrophil count (ANC) < 1500 cells/ μL (< 1200 cells/ μL for subjects of African descent who are black).
 - Indirect bilirubin $> 1.5 \times \text{ULN}$ and direct bilirubin $> \text{ULN}$.

Investigational Product: ombitasvir/ABT-450/ritonavir: 12.5 mg/75 mg/50 mg tablet

sofosbuvir: 400 mg tablet

ribavirin: 200 mg tablet

Dose: ombitasvir/ABT-450/ritonavir: 25 mg/150 mg/100 mg QD

sofosbuvir: 400 mg QD

ribavirin weight-based dosing 1000 to 1200 mg BID

Mode of Administration:	Oral
Reference Therapy:	Not applicable
Dose:	Not applicable
Mode of Administration:	Not applicable
Duration of Treatment:	Subject will receive multiple QD doses of ombitasvir/ABT-450/r co-administered with SOF with or without RBV BID for 12 weeks.
Criteria for Evaluation:	
Efficacy:	Plasma HCV RNA in IU/mL will be assessed at all Treatment Period visits and at all PT visits.
Criteria for Evaluation (Continued):	
Patient Reported Outcomes (PROs):	Health State Utility will be assessed using the EuroQol-5 Dimensions-5 Level (EQ-5D-5L) including its Visual Analog Scale (VAS) component. Fatigue severity will be assessed using the Fatigue Severity Scale (FSS) including its Visual Analog Fatigue Scale (VAFS) component.
Resistance:	The following information will be tabulated and summarized: 1) for all subjects, the variants at baseline at signature resistance-associated amino acid positions relative to the reference sequence, and 2) for subjects who do not achieve SVR ₁₂ , all post-baseline variants relative to baseline.
Pharmacokinetic:	Intensive pharmacokinetic samples will be collected on Day 1 at 2, 4, and 6 hours post DAA dosing and at the 2-week visit at pre-dose and approximately 2, 4, and 6 hours post DAA dose for measurement of concentrations of ombitasvir, ABT-450, ritonavir, SOF, GS-331007 (predominant circulating metabolite of SOF), and RBV (if applicable). In addition, pharmacokinetic samples will be collected at each study visit during treatment.
Safety:	Safety and tolerability will be assessed by monitoring adverse events, physical examinations, clinical laboratory tests, 12-lead ECGs, and vital signs.
Statistical Methods:	
Efficacy:	The primary endpoint is the percentage of subjects with SVR ₁₂ (HCV RNA < LLOQ 12 weeks after the last actual dose of study drugs). The secondary endpoints are the percentage of subjects with virologic failure during treatment and the percentage of subjects with relapse post-treatment. For the primary and secondary endpoints, the simple percentage of subjects meeting the endpoint will be calculated, and a 2-sided 95% Wilson score confidence interval for a binomial proportion will be computed.

Statistical Methods (Continued):**PROs:**

Changes from baseline in the EQ-5D-5L health index score, the visual analogue scale (VAS) response component of the EQ-5D-5L, FSS score, and visual analogue fatigue scale (VAFS) component of the FSS will be summarized for each applicable post-baseline visit by overall and by treatment arm, respectively.

Resistance:

The following resistance information will be provided for all subjects: the amino acid variants at baseline at signature resistance-associated positions identified by population nucleotide sequencing and comparison to the appropriate prototypic reference sequence.

The following resistance information will be analyzed for subjects who do not achieve SVR₁₂ and who have a post-baseline sample with HCV RNA \geq 1000 IU/mL: 1) the amino acid variants in available post-baseline samples identified by population and/or clonal nucleotide sequencing and comparison to the baseline sequence, 2) the amino acid variants in available post-baseline samples at signature resistance-associated positions identified by population nucleotide sequencing and comparison to the appropriate prototypic reference sequence, and 3) the persistence of resistance-associated amino acid variants by population and/or clonal nucleotide sequencing during the post-treatment period.

Pharmacokinetic:

Individual plasma concentrations of ABT-450, ritonavir, ombitasvir, SOF, GS-331007, and ribavirin will be tabulated and summarized. Individual plasma concentrations of possible metabolites of ABT-450, ombitasvir, and SOF (other than GS-331007) may be tabulated and summarized if measured and sufficient levels of metabolites are observed.

Values for the pharmacokinetic parameters of ombitasvir, ABT-450, ritonavir, SOF, GS-331007, and RBV (if applicable) including the C_{max} , T_{max} , C_{trough} , and AUC will be determined by noncompartmental methods using intensive pharmacokinetic blood sampling data in the study. Additional parameters or summaries may be determined if useful in the interpretation of the data.

Safety:

The number and percentage of subjects reporting treatment-emergent adverse events will be tabulated by Medical Dictionary for Regulatory Activities (MedDRA) system organ class and preferred term for each treatment arm and overall. Tabulations by treatment arm will also be provided in which the number of subjects reporting a treatment emergent adverse event (MedDRA preferred term) is presented by severity (mild, moderate, or severe) and relationship to study drugs.

Change from baseline in laboratory tests and vital sign measurements to each time point of collection will be summarized descriptively for each treatment arm. Laboratory test and vital sign values that are potentially clinically significant, according to predefined criteria, will be identified and the number and percentage of subjects with potentially clinically significant values during treatment will be calculated for each treatment arm.

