5.0 Investigational Plan**5.1 Overall Study Design and Plan: Description**

This is a Phase 2, randomized, open-label, multicenter study evaluating the safety and efficacy of co-formulated ombitasvir/ABT-450/r co-administered with SOF with or without RBV in treatment-naïve and prior (pegIFN, RBV, and/or SOF) treatment-experienced adults with genotype 3 HCV infection without cirrhosis. Approximately 20 subjects will be enrolled across approximately 8 sites globally into one of two treatment arms ([Figure 1](#)).

Figure 1. Study Design

These subjects will be randomized to Arms A and B in a 1:1 ratio (approximately 10 subjects each). Randomization to Arms A and B will be stratified by IL28B genotype (CC versus non-CC) and prior treatment status (treatment-naïve versus treatment-experienced).

- **Arm A:** ombitasvir/ABT-450/r 25 mg/150 mg/100 mg and SOF 400 mg QD for 12 weeks
- **Arm B:** ombitasvir/ABT-450/r 25 mg/150 mg/100 mg and SOF 400 mg QD with RBV 1000 – 1200 mg BID for 12 weeks

RBV dosing will be weight-based, either 1000 mg or 1200 mg daily divided BID per local label (e.g., < 75 kg = 1000 mg daily divided BID or ≥ 75 kg = 1200 mg daily divided BID).

The duration of the study will be up to 60 weeks long (not including a screening period of up to 35 days) consisting of two periods: the Treatment Period and the Post-Treatment (PT) Period. All subjects who complete or prematurely discontinue the Treatment Period will be followed for 48 weeks to monitor safety, HCV RNA, the persistence of resistant viral mutants, and assessment of Patient Reported Outcomes (PROs).

Subjects will be either HCV treatment-naïve or previously treated with interferon, pegIFN, RBV, and/or SOF. Categorization of prior HCV treatment experience will be based on the last prior HCV treatment course. This prior HCV therapy must have been completed no less than 2 months prior to the Screening Visit.

Subjects whose only prior treatment experience included standard (non-pegylated) interferon will not be eligible. However, subjects with a prior history of non-pegylated interferon therapy who were subsequently treated with pegIFN/RBV, pegIFN/RBV plus SOF, or SOF plus RBV may be enrolled.

Subjects with previous HCV RNA measurements that provide complete documentation of the type of response to prior treatment with pegIFN/RBV without sofosbuvir, pegIFN/RBV plus sofosbuvir, or sofosbuvir plus RBV therapy will be categorized as one of the following:

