5.5.4 Selection and Timing of Dose for Each Subject

Study drug dosing will be initiated at the Study Day 1 Visit. Ombitasvir/ABT-450/r and SOF will be dosed QD. Thus with normal dosing, 2 ombitasvir/ABT-450/r tablets and 1 SOF tablet should be taken in the morning.

RBV (if applicable) should be dosed BID, e.g., 2 or 3 tablets taken in the morning, and 3 RBV tablets should be taken in the evening. Subjects with renal impairment should receive a reduced dose of RBV, as described below ([Table 8](#)).

Table 8. Recommended Ribavirin Dosing in Chronically HCV-Infected Patients with Chronic Kidney Disease

Renal Impairment and Creatinine Clearance, mL/min	Renal Severity	RBV Dose (mg/day)
Normal (> 80 mL/min)	None	1000/1200
CKD Stage 3 (30 – 50 mL/min)	Moderate	200 alternating with 400
CKD Stage 4 (< 30 mL/min)	Severe	200

Note: Brennan et al.²⁵

All study drugs should be dosed together and administered with food.

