The maximum RBV dose administered in this study will not exceed 1200 mg, divided twice daily for 12 weeks. RBV dosage will be reduced in subjects with a calculated creatinine clearance < 50 mL/min (Section 6.7.6).

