4.2 Design Diagram

This is a Phase 2, randomized, open-label, multicenter study evaluating the efficacy and safety of co-administration of ombitasvir/ABT-450/r with SOF with or without RBV administered for 12 weeks in HCV GT3 (with and without cirrhosis) and 8 and 6 weeks for GT2 (without cirrhosis) infected, treatment-naïve and treatment-experienced (previous pegIFN/RBV and/or SOF) adults. Approximately 70 subjects will be enrolled at approximately 8 sites globally.

[figure not shown]
Treatment Period and Post-Treatment Period

Approximately 20 GT3 subjects without cirrhosis meeting the eligibility criteria will be randomized 1:1 into Arm A and Arm B and treated as below:

- Arm A: ombitasvir/ABT-450/ritonavir 25/150/100 mg once daily (QD) and SOF 400 mg (QD) for 12 weeks;
- Arm B: ombitasvir/ABT-450/ritonavir 25/150/100 mg once daily (QD) and SOF 400 mg (QD) with RBV 1000 – 1200 mg divided twice daily (BID) per local label for 12 weeks.

Randomization to Arms A and B will be stratified by IL28B genotype (CC versus non-CC) and prior treatment status (treatment-naïve versus treatment-experienced).

Approximately 10 GT2 subjects meeting the eligibility criteria will be enrolled in to each of Arm C and Arm D and treated as described below. Arm D would be launched if no more than one subject who completes treatment in Arm C experiences relapse through PT Week 4.

Figure 1. Study Schematic

- Arm C: ombitasvir/ABT-450/ritonavir 25/150/100 mg once daily (QD) and SOF 400 mg (QD) with weight based RBV 1000 – 1200 mg BID per local label for 8 weeks;

- Arm D: ombitasvir/ABT-450/ritonavir 25/150/100 mg once daily (QD) and SOF 400 mg (QD) with weight based RBV 1000 – 1200 mg BID per local label for 6 weeks;

Approximately 20 subjects with genotype 3 HCV infection with compensated cirrhosis (a minimum of approximately 20% will be treatment-experienced) will be enrolled into Arm E:

- Arm E: ombitasvir/ABT-450/r 25 mg/150 mg/100 mg and SOF 400 mg QD with RBV 1000 – 1200 mg BID for 12 weeks

An additional 10 subjects with genotype 3 HCV infection without cirrhosis will be enrolled in open-label fashion into Arm F:

- Arm F: ombitasvir/ABT-450/r 25 mg/150 mg/100 mg and SOF 400 mg QD for 12 weeks

RBV dosing will be weight-based, either 1000 mg or 1200 mg daily divided BID per local label (e.g., < 75 kg = 1000 mg daily divided BID or ≥ 75 kg = 1200 mg daily divided BID).

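### Ribavirin is written as 1000–1200 mg BID in five places, against a divided daily total capped at 1200 mg elsewhere, and the renal dosing passages do not agree with each other

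*Protocol*

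**What the plan says.** **Dose.** Five statements give a dose with BID and do not say that it is a daily total:
- Protocol synopsis, Dose line: "ribavirin weight-based dosing 1000 to 1200 mg BID".
- Protocol 5.1, Arm B: "SOF 400 mg QD with RBV 1000 – 1200 mg BID for 12 weeks".
- SAP 4.2, Arm C: "with weight based RBV 1000 – 1200 mg BID per local label for 8 weeks". Arm D has the same form for 6 weeks, and Arm E for 12 weeks.

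Other statements give a daily total split over two intakes. The synopsis definition of Arm B has "RBV 1000 – 1200 mg divided twice daily (BID) for 12 weeks", and SAP Arm B is also worded as divided. Protocol 5.1 (just after the arm list), 5.1.2, 5.5.1 and 5.6.4, and the sentence closing the arm list in SAP 4.2, all give 1000 or 1200 mg per day by weight, in two parts. Protocol 5.6.4 adds: "The maximum RBV dose administered in this study will not exceed 1200 mg, divided twice daily for 12 weeks".

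**Renal function.** Protocol 5.5.4 sends subjects with renal impairment to Table 8 for a reduced dose. As read from the PDF, Table 8 has rows for above 80, for "CKD Stage 3 (30 – 50 mL/min"), and for below 30 mL/min. Protocol 5.5.1 applies the reduction from 30 up to, but not including, 50. Protocol 5.6.4 reduces below 50. Table 9 (Section 6.7.4) separates 50 and above from below 50. Table 10 (Section 6.7.6) has rows for 30–50, below 30 and hemodialysis. Exclusion criterion 16 bars only clearance below 30.

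**The concern.** The five statements sit where a reader looks for the regimen: the synopsis Dose line and the arm definitions. In the synopsis, the two lines above the ribavirin line give the other drugs as an amount per intake followed by a frequency. Read the same way, the ribavirin line means 1000 to 1200 mg at each of two intakes. The synopsis, Protocol 5.1 and SAP 4.2 therefore each contradict themselves. On the SAP's planned numbers, Arms C, D and E are about 40 of the roughly 50 subjects in ribavirin arms.

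The protocol itself attributes anemia in earlier trials largely to ribavirin and says that hemoglobin declines were largely managed by reducing its dose (Section 3.0). A regimen statement for this drug should have one meaning.

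The renal passages raise the same question on a smaller scale. A site could find no row in Table 8 for an eligible subject, or find that two passages disagree at a boundary.

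**Working it through.** **1. Stated daily dose, reproduced.** Inputs: 200 mg tablets (Protocol 5.5.1); 2 or 3 tablets in the morning and 3 in the evening (5.5.4).
- (2 + 3) × 200 = 1000 mg/day
- (3 + 3) × 200 = 1200 mg/day

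These match the two weight bands and the 1200 mg maximum.

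**2. Literal BID reading.**
- 2 × 1000 = 2000 mg/day, or 10 tablets; 2000/1200 = 1.67 times the maximum
- 2 × 1200 = 2400 mg/day, or 12 tablets; 2400/1200 = 2.0 times the maximum

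Each is exactly twice the stated daily dose of its own weight band.

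**3. Drug supply.** A ribavirin bottle holds 168 tablets and a sofosbuvir bottle 28 (Protocol 5.5.2.1).
- Ribavirin at 6 a day: 168/6 = 28 days
- Sofosbuvir at 1 a day: 28/1 = 28 days
- Ribavirin at 12 a day: 168/12 = 14 days

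The supply fits the divided daily total.

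**4. Renal coverage, value by value.**

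| Creatinine clearance (mL/min) | Row in Table 8 | Reduced under the text of 5.5.1 and 5.6.4? | Group in Table 9 |
|---|---|---|---|
| 30 | 30–50 | yes | < 50 |
| 49.9 | 30–50 | yes | < 50 |
| 50 | 30–50 | no | ≥ 50 |
| 50.1, 65, 80 | none | no | ≥ 50 |
| 80.1 | > 80 | no | ≥ 50 |

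At exactly 50, the Table 8 row alternates 200 and 400 mg, a mean of (200 + 400)/2 = 300 mg/day. The unreduced dose is 1000/300 = 3.3 to 1200/300 = 4 times that. Table 10 has the same 30–50 label. However, Section 6.7.6 leads to that table only after a confirmed fall below 50, or below 30 for a subject who began under 50, so the conflict at 50 lies mainly in Table 8.

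**5. Cross-references.** Protocol 5.5.1 cites Section 6.7.6 together with Table 9 for renal dosing, but the renal table in that section is Table 10. The note under Table 10 cites Table 8 for clearance below 50 with hemoglobin below 10, but that rule is in Table 9.

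**The case against.** The strongest reply is that nobody would dose from the short form. The administration sections (5.5.1 and 5.5.4) give the daily total and count the tablets, the bottle size agrees, the maximum is explicit, and in both documents a sentence after the arm definitions spells out the split. The SAP is not a dosing document. All of this stands. A reader might infer that subjects would receive double the dose; that would require setting aside all of these statements.

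A reader might also infer that compliance would be miscounted: 84 × 6 = 504 tablets taken against 84 × 12 = 1008 expected gives 50%, below the 80% limit in SAP 9.2. The documents do not support this. SAP 9.2 counts the tablets due under the protocol, and Protocol 5.5.4 puts that at 5 or 6 a day.

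On renal function, the reply is that Table 8 is attributed to a cited publication, that a row may have been lost in reading the PDF, and that the text and Table 9 already treat 50 and above as one group. So it would go too far to say that subjects between 50 and 80 have no guidance. What remains is that 5.5.4 sends subjects with renal impairment to a table that labels only values above 80 as normal and has no row for this band. The conflict at exactly 50 and the two wrong cross-references do not depend on a lost row.

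**Conclusion.** The contradiction in the ribavirin dose is real and is one of wording. Five regimen statements, read literally, give twice each weight band's stated daily dose and 1.67 to 2 times the stated maximum. The factor of 2 against the maximum holds only at 1200 mg; at 1000 mg it is 1.67. Not every arm definition is affected, since Arm B in the synopsis and in the SAP is worded as divided. Administration above the maximum is unlikely, and no endpoint, sample size or compliance result is shown to change. The point merits correction because it concerns the treatment definition of a drug whose anemia the protocol manages by dose.

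The renal inconsistency is narrower: a gap in one table for values above 50 and up to 80, one boundary value with conflicting instructions, and two misdirected references. The gap rests on Table 8 having been read completely from the PDF.

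**What to change.** The sponsor should:
- reconcile the synopsis Dose line, Arm B in Protocol 5.1 and Arms C, D and E in SAP 4.2 with the other ribavirin statements, and use one statement throughout;
- reconcile Tables 8 and 10 with Protocol 5.5.1, 5.6.4 and Table 9, so that each eligible creatinine clearance value is covered once, including 50 and the band from 50 to 80;
- correct the reference to Table 9 in 5.5.1 and the reference to Table 8 in the note under Table 10.

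The sponsor decides the values; none is proposed here. The cost is wording changes in the protocol and SAP, with no change to the statistical analyses.
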